The study procedures outlined below cover 3 integrated experiments. A general overview of each study suggests a highly integrated set of experiments that will help explain neuromodulatory effects. **Study 1** investigates the effects of **frequency** and number of pulses, manipulated across blocks. rTMS is applied to MT or the vertex at 7 doses consisting of up to 30 pulses at 1, 5, or 10Hz. **Study 2** manipulates the **location** and orientation of the coil during rTMS of MT to bias rTMS effects either toward the dorsal pathway or toward the ventral pathway. **Study 3** manipulates **brain state** and uses *motion task blocks*, as in Studies 1 and 2, but also *color task blocks* and *rest blocks*. As in Study 2, only 5Hz rTMS is used. Therefore, we describe first the *shared* design information, and then describe design information *specific* to each of the 3 Studies.

Table 1. TIMELINE OF STUDY PROCEDURES:

Assessment	Screening Session	Session 1 (Shared)	Session 2 or 3 TMS-fMRI	Session 2 or 3 TMS-EEG
1. Subject consent & questionnaires	X			
2. Urine Test	X			
3. Practice with Motion task	X			
4. TMS Tolerability	X			
5. TMS Motion disruption, phosphene and motor thresholds	X			
6. Structural MRI (T1 & DWI)		X		
7. Resting-state fMRI		X		
8. Event-related fMRI with Motion task		X		
9. Concurrent TMS-fMRI with Motion task			X	
10. Concurrent TMS-EEG with Motion task				X
11. Side Effect Checklist	X		X	X

The Table above presents the timeline of major study procedures.

Shared Design Details

Subject Screening. In each of the 3 studies proposed, 48 different healthy young adults (18-30 y.o.) will participate in both TMS-MRI and TMS-EEG components of each study. Participants will have no psychiatric or neurological history and no ongoing psychoactive drug use (for more details see Section 5 below). Normal right-handed volunteers will be recruited from the community.

Each participant will take part in up to **seven** sessions: the first two sessions are *shared* by the TMS-MRI and TMS-EEG components of each study. The third and fourth sessions correspond separately to the TMS-fMRI and TMS-EEG sessions—with designs specific to each of the 3 Experiments—with the order counterbalanced across participants. If participants have been included in the pilot protocol, they will have two additional visits. Finally, an additional visit is built in if subjects need to make up a visit (e.g. poor task performance).

[figure not shown]

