Shared Session 1: Screening. During Session 1 participants will be screened for the study with the rTMS screening forms (demographics, health, etc.), BIAC screening form, and a urine test. If they pass the screening procedure, they will proceed to the to the TMS Service Center, where motor threshold will be defined; and where they will learn and practice the motion tasks used in the study (about 0.5 hr) during visual cortex stimulation in order to acclimate them to rTMS and to obtain phosphene, motion disruption thresholds, for future dosing of rTMS. The motion task in the screening visit will consist of the second phase (motion period) of the task described below.

Shared Session 2: MRI Scanning. During Session 2 (2 hrs), participants undergo a 60-min MRI session. At BIAC, after obtaining a structural MRI and DTI and resting-state fMRI scans, fMRI data will be recorded from subjects while they perform the Motion task. BOLD images will be acquired with a 3.0T GE MR Scanner. Stimuli will be back-projected onto a screen located at the head of the MRI bed using an LCD projector. Subjects will view the screen via a mirror system located in the head coil. Task onset will be electronically synchronized with the MRI acquisition computer.

Shared Motion Task: All three Studies use the same motion task but manipulate different factors. Every trial consists of three phases (**Fig. 1A**): stimulation, motion, and inter-trial interval. Here we describe the task with rTMS—practice versions and fMRI versions of the Motion Task are identical, minus the delivery of rTMS.

1. Stimulation period (3 s).

Subjects view two circles on either side of fixation, each filled with stationary random dots, while receiving rTMS to right MT or vertex. When an rTMS burst is briefer than 3 s, its onset is delayed so it co-terminates with the stimulation period (e.g., a 1.5-s rTMS burst is delayed by 1.5 s). rTMS is delivered to MT at a value not to exceed 120% of

individualized motor threshold, an intensity that yields both inhibitory and excitatory effects for brief trains (Gerschlager et al., 2001; Modugno et al., 2001; Fitzgerald et al., 2002; Lang et al., 2006) and has been shown to be within the published safety guidelines (Rossi et al., 2009b).

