Piloting of the Motor Tasks and rTMS: In order to ensure success of the design proposed above, it will be critical to determine the proper timing of the rTMS effect. It is critical to determine the optimum stimulation onset to provide the maximal benefit to participants' working memory performance. As such, we plan to recruit 264 younger adults in an abbreviated version of the design for each Study presented above (88 participants per Study). Study procedures will be **identical** to those described above in **Table 1**, excluding Steps 6-10, which include MRI scanning. We will therefore rely on a non-MRI-based 10-20 system; while not as effective as fMRI-based targeting, using the 10-20 system for TMS positioning is applicable at low cost and may reach desired cortex regions reliably on a larger scale level (Herwig et al., 2003). Timing parameters for each piloting session are identical to those described above for **Study1/Study2/Study3**.

5. Selection of Subjects:

In each of the 3 studies proposed, 48 healthy young adults (18-30 y.o.) will participate in both TMS-MRI and TMS-EEG components of each study.

Study Inclusion Criteria:

1. Age restrictions
 - a. Age between 18-30.
2. Use of effective method of birth control for women of childbearing capacity.
3. Willing to provide informed consent.

Study Exclusion Criteria (ascertainment when appropriate):

1. Current or recent (within the past 6 months) of substance abuse or dependence, excluding nicotine and caffeine (urine test).
2. Current serious medical illness (self report).
3. History of seizure except those therapeutically induced by ECT (childhood febrile seizures are acceptable and these subjects may be included in the study), history of epilepsy in self or first degree relatives, stroke, brain surgery, head injury, cranial metal implants, known structural brain lesion, devices that may be affected by rTMS or MRI (pacemaker, medication pump, cochlear implant, implanted brain stimulator); [TMS Adult Safety Screening (TASS) form].
4. Subjects are unable or unwilling to give informed consent.
5. Diagnosed any Axis I DSM-IV disorder (MINI, DSM-IV)
6. Subjects with a clinically defined neurological disorder including, but not limited to:
 - a. Any condition likely to be associated with increased intracranial pressure
 - b. Space occupying brain lesion.
 - c. History of stroke.

- d. Transient ischemic attack within two years.
- e. Cerebral aneurysm.
- f. Dementia.

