- g. Mini Mental Status Exam (MMSE) score of <24.
- h. Parkinson's disease.
- i. Huntington's disease.
- i. Multiple sclerosis.
- 7. Increased risk of seizure for any reason, including prior diagnosis of increased intracranial pressure (such as after large infarctions or trauma), or currently taking medication that lowers the seizure threshold.
- 8. Subjects with cochlear implants
- 9. Subjects not willing to tolerate the confinement associated with being in the MRI scanner.
- 10. Women who are pregnant or breast-feeding (urine test).
- 11. Blindness.
- 12. Inability to read or understand English.

6. Subject Recruitment & Compensation:

We will recruit 264 total subjects into our 3 Studies. Prior to the main experiment for each Study, we will recruit pilot subjects to refine the experimental procedure and ensure adequate power (n=40 for each of 3 Studies, n=120 total). Then, for the main experiments, 48 subjects will be recruited for each study (n=144 total). Thus, 48 volunteers will be recruited for each Study, half male, half female, in order to achieve three groups of 38 completers for each study, given a 20% drop-out rate.

Subject Recruitment: Neurologically normal volunteers will be recruited from either a subject pool maintained at the BIAC for MRI (IRB protocol Pro00010672), [the](#) IBRC SONA site, Duke List (www.dukelist.edu), Craigslist, or flyers distributed on campus locations. Additionally, subjects who have participated in another active TMS Study (Protocol 000065334) and have explicitly indicated a willingness to be contacted for future experiments, may be contacted for participation in the current protocol. Male and female subjects from all racial and minority groups will be accepted.

Subject payment: \$20 per hour, approximately \$300.00 total for screening session (2 hrs), MRI session (2 hrs), and up to 4 additional sessions pairing TMS with another data collection technique (2 hrs each). 15 hours represents the maximum possible participation, including piloting and the full study, with the possibility of making up one visit. Payment will be made by via direct deposit for individuals with a Duke Unique ID or by check sent by mail within a few weeks after the end of their study involvement.

7. Consent Process:

Section 14 questions have been completed on the e-IRB submission form.

8. Subject's Capacity to Give Legally Effective Consent:

N/A: Only involves healthy volunteers

9. Study Interventions:

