Participation is voluntary, and there will be no pressure or time constraints regarding the decision to participate. There are no benefits to the participants except for the monetary reward or compensation, as well as the good will of helping the progress of scientific research. The information learned from this study may aid our understanding of the mechanisms of action underlying TMS and the dose-response relationships between stimulation and neural activity.

MRI Adverse Events Plan:

An MRI procedure is considered to be "minimal risk" according to federal definitions. To date, no after effects have been revealed and the FDA has classified the MR procedure as possessing a "non significant risk" for the subject of study. To minimize risks, all subjects will be screened for metallic devices, implants and other contraindications to scanning. Women of child-bearing capacity will be evaluated for pregnancy using a urine pregnancy test prior to scanning. Those unlikely to tolerate the sense of confinement during scanning will also be excluded.

Adequate safety monitoring and observation during scanning will be provided, as will measures to enhance the subject's physical and emotional comfort during the scan. It is possible that some subjects might experience minor distress by the confined and noisy conditions in the scanner. This possibility will be minimized by earplugs and headphones, and experienced technicians who will monitor all subjects for distress. In the event that a subject becomes anxious during a scan, the study will be halted. Subjects will be able to communicate with the investigators at all times using the intercom system should they wish to request that a study be terminated or have

concerns or questions during the procedure. The subject is in full view of the operator at all times.

The probability of an incidental finding that might lead to the diagnosis of an unknown abnormality is greater than zero. All subjects will be alerted to this possibility during the consent process. In that event, subjects or their designated physician will be provided copies of their anatomical scans and advised to seek further evaluation if they have concerns.

EEG Adverse Events Plan

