Risks to the unborn children of pregnant women receiving MRI and rTMS are unknown. Pregnant women will be excluded as per IRB policy. Female subjects are tested once with a urine pregnancy test prior to their first MRI session as per IRB-approved BIAC policy. These female subjects agree not to become pregnant while remaining within the subject pool, and to notify the experimenter or subject coordinator if they become pregnant. If sexually active, the subject must agree to use appropriate contraceptive measures for the duration of the study. Medically acceptable contraceptives include: (1) surgical sterilization (such as a tubal ligation or hysterectomy), (2) approved hormonal contraceptives (such as birth control pills, patches, implants or injections), (3) barrier methods (such as a condom or diaphragm) used with a spermicide, or (4) an intrauterine device (IUD). Contraceptive measures such as Plan B (TM), sold for emergency use after unprotected sex, are not acceptable methods for routine use. If the subject has any uncertainty about whether they could be pregnant, another urine pregnancy test will be performed before they can participate in this protocol. The person(s) who will perform the urine pregnancy test will have successfully completed training as directed by the Chair of Obstetric and Gynecology of the Duke University School of Medicine. The urine pregnancy test kits used for this research study will be those commercially available test kit specified by the Chair of Obstetric and Gynecology and in routine use at DUHS.

11. Costs to the Subject:

There is no cost for subjects to participate in this study.

12. Statistical Analysis Plan:

Shared Analytical Procedures

fMRI analyses. fMRI data are inspected for head motion and data quality using custom BIAC software. Multiple regression analyses use FSL (FMRIB's Software Library, www.fmrib.ox.ac.uk/fsl) FEAT tool (FMRI Expert Analysis Tool). Physiological noise is accounted for in our models by using FSL's PNM toolbox, with a model optimized for brainstem signals. Initial multiple regression analyses are conducted on individual runs, and then across runs for individual participants using a fixed-effects analysis. These analyses are combined across participants within each group using random-effects analyses implemented via FSL's FLAME tool. Between-group comparisons are controlled for multiple comparisons using an FDR alpha set to < 0.05 .

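### Exclusions that can change over time have a scheduled check only at screening, and an incidental MRI finding is not linked to the lesion exclusions before the main rTMS sessions

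*Combined protocol and SAP*

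**What the plan says.** **Exclusions (Section 5).** Criterion 1 covers current or recent substance abuse or dependence, with a six-month window. Criterion 7 includes anyone "currently taking medication that lowers the seizure threshold". Criterion 10 covers pregnancy and breast-feeding. Criterion 3 lists, among other things, a "known structural brain lesion", ascertained by the TMS Adult Safety Screening form. Criterion 6b lists a space-occupying lesion.

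**Schedule (Section 4).** Table 1 marks the row "Subject consent & questionnaires" and the urine-test row in the Screening column only. The text agrees: at the screening session "participants will be screened for the study with the rTMS screening forms (demographics, health, etc.), BIAC screening form, and a urine test". The only Table 1 row marked both at screening and at the two later TMS sessions is "11. Side Effect Checklist". The structured interview held before and after rTMS is described as an assessment of side effects.

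**Pregnancy (Section 10).** The TMS Adverse Events Plan states: "Female subjects are tested once with a urine pregnancy test prior to their first MRI session as per IRB-approved BIAC policy". It adds that women agree to report a pregnancy, and that the test is repeated if the woman herself is unsure. The MRI Adverse Events Plan says only that women of child-bearing capacity are tested before scanning. It does not say whether that means the first scan or every scan.

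**Incidental findings (Section 10).** If the MRI shows an unknown abnormality, "subjects or their designated physician will be provided copies of their anatomical scans and advised to seek further evaluation if they have concerns".

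**The concern.** A check at screening describes the participant on that day. Criteria 1, 7 and 10 concern current or recent status, and most of the stimulation is delivered at later visits. A volunteer who starts a relevant drug or becomes pregnant after screening meets no scheduled question that would bring this to light before the next rTMS session.

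The protocol's own safety argument depends on this screening. The TMS Adverse Events Plan cites a consensus report in which many of the newer seizure cases were in patients on drugs that may lower the seizure threshold, and then relies on screening for known risk factors. It also says that the risks of MRI and rTMS to an unborn child are unknown. The participants are healthy volunteers who gain nothing beyond payment and the good will of helping research.

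The MRI raises a related question. It is acquired after screening and before the main rTMS sessions, and it is used to choose the stimulation target. A lesion seen on it is arguably then known in the sense of criterion 3. Yet the stated response leaves follow-up to the participant and does not mention eligibility for the remaining sessions.

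**Working it through.** The plan gives no figure to reproduce. The check is a trace of each exclusion through the schedule, plus a count of sessions. Table 1 and the Section 4 text number the sessions differently, so they are named here by content.

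**Session count.** Section 4 allows up to seven visits: 2 shared (screening, MRI) + TMS-fMRI + TMS-EEG + 2 pilot + 1 make-up = 7, which agrees with the text.

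**Core rTMS sessions.** Screening (tolerability, thresholds, practice with stimulation), TMS-fMRI and TMS-EEG = 3. The shared MRI visit has no rTMS.

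| Core rTMS session | Questionnaires, screening forms, urine test | Side-effect checklist |
|---|---|---|
| Screening | yes | yes |
| TMS-fMRI | none scheduled | yes |
| TMS-EEG | none scheduled | yes |

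Sessions without a scheduled recheck: 3 − 1 = 2, so 2 of 3.

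**How much stimulation follows the check.** In Study 1 there are 40 trials per condition, and Table 2 gives 3, 15, 30, 15, 3, 3 and 30 pulses for the seven conditions. Per session: 40 × (3 + 15 + 30 + 15 + 3 + 3 + 30) = 40 × 99 = 3,960 pulses. Over TMS-fMRI and TMS-EEG: 2 × 3,960 = 7,920. All of these come after the only scheduled check.

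**Each changeable exclusion after screening.**

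| Exclusion | Scheduled recheck | Other stated safeguard |
|---|---|---|
| 1, substance abuse or dependence | none | none |
| 7, seizure-threshold medication | none | none |
| 10, pregnancy | none, if tested once is taken at its word | contraception, duty to notify, repeat test if the participant is unsure |

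**MRI finding.** Exclusions 3 and 6b name lesions. The incidental-finding paragraph names copies and advice. Eligibility steps stated between the two: 0.

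**Pregnancy wording.** If a test before scanning means every scan, the MRI plan requires a further test before TMS-fMRI, since that is also a scan. That conflicts with a single test in the TMS plan and with Table 1, and still leaves TMS-EEG without one. If it means the first scan only, the statements agree and no later test is scheduled.

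**What cannot be computed.** No interval between sessions is stated, nor any rate at which participants start medication, become pregnant or show MRI abnormalities. The chance of becoming ineligible is therefore not estimable from the documents.

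**The case against.** **Table 1 is weak evidence alone.** It is presented as a timeline of major procedures and omits the mood ratings that the text schedules. That is fair, but the Section 4 text also places the forms and urine test at screening, and Section 10 says the pregnancy test is done once.

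**Other safeguards exist.** Section 10 says that the safety guidelines are built into screening and session procedures. Section 13 has a monitor who reviews charts, confirms eligibility for each enrolled participant and meets quarterly. Neither describes a check before a given rTMS session. The pregnancy safeguards are real, but they depend on the participant acting and do not extend to medication or substance use.

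**Unseen documents may fill the gap.** The screening forms, the imaging centre's policy and the interview form could contain questions at each session. This stands. If they do, citing them in the schedule largely settles the recheck point.

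**Stronger readings that a reader might infer, and that the documents do not support:**

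- *The pregnancy test comes too late, after rTMS at screening.* A urine test at screening also precedes the first MRI, and participants go on to stimulation only if they pass screening.
- *Pilot participants, who have no MRI, are never tested.* The piloting text drops only steps 6 to 10 of Table 1. The questionnaires and urine test remain.
- *Giving rTMS before the structural scan contradicts the lesion exclusions.* Criterion 3 concerns a known lesion, ascertained by form, and criterion 6 a clinically defined disorder. Both can be applied from history.
- *Up to 5 of 6 rTMS sessions are unchecked.* This requires both pilot visits and the make-up visit to deliver rTMS, and a participant in both phases to be screened only once. The pilot keeps its own screening steps, and a make-up could be the MRI visit.

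**Conclusion.** The point holds as a gap in the safety schedule that should be closed. As written, 2 of the 3 core rTMS sessions, including all of the main experimental stimulation, take place with no scheduled investigator-led recheck of exclusions 1, 7 and 10. The response to an incidental MRI finding is not connected to exclusions 3 and 6b. The two statements on pregnancy testing in Section 10 need to be reconciled with each other and with Table 1.

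This rests on the visible text and assumes that no attached form or policy already requires a check at each session. It does not show that any participant would in fact receive rTMS while ineligible, or how likely that is. The population is healthy, aged 18 to 30 and without psychiatric or neurological history. The point concerns participant protection, not the validity of the analyses.

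**What to change.** 1. In Table 1, extend the questionnaire part of the first row to the TMS-fMRI visit, the TMS-EEG visit and any make-up visit with rTMS. Re-administer the existing TMS safety form alongside the pre-session interview, and apply the existing Section 5 exclusions to the answers. If an attached form already does this, cite it in the schedule instead.
2. Reconcile the incidental-finding paragraph in Section 10 with exclusions 3 and 6b, so that the plan says how a finding on the shared MRI scan bears on eligibility for later sessions.
3. Reconcile the MRI and TMS Adverse Events Plans with each other and with Table 1 on when pregnancy testing is due.

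The sponsor and IRB decide the rules and timing under each item; this review proposes none.

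**Cost.** A few minutes per visit with a form already in use, plus protocol wording. The form is still self-report, but prompted and documented. An occasional session will be postponed or a participant withdrawn. Withdrawals would come out of the 20% drop-out already allowed (48 × 0.8 = 38.4, stated as 38 completers per study). In Study 1 the plan states that 30 are sufficient, a margin of 38 − 30 = 8.

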Research Protocol Summary

1. Protocol Title: Effects of rTMS on human brain activity measured with EEG and fMRI

Note: This protocol covers three studies (Aims 1-3) of a NIMH BRAIN R01 grant supporting this research currently under review.

2. Purpose of the Study:

Treating psychiatric and motor disorders without surgery or life-long pharmacology is a vexing but attainable goal. One avenue of progress has been the development of non-invasive brain stimulation methods such as repetitive transcranial magnetic stimulation (rTMS). This project investigates the effects of rTMS on neural circuits as a function of spatiotemporal parameters and brain state in order to better understand why the method works and how to improve its efficacy. Leveraging our expertise in application of TMS methodology during concurrent single neuron recording techniques in non-human primates and imaging and scalp potential techniques in humans (fMRI and EEG), we aim to resolve three interlocking problems in the design and application of rTMS: **stimulation frequency, spatial targeting, and interactions with brain state.**

Primary Objective: Investigate rTMS temporal parameters: impact of frequency (1Hz versus 5Hz versus 10Hz rTMS) and number of pulses.

Primary Endpoint: We make 2 general predictions. **(1)** 1Hz vs. 5/10Hz rTMS will have inhibitory vs. excitatory effects on behavior (reaction times—RTs) and motion-related (high vs low coherence) medial temporal (MT) activity (in both EEG, and fMRI). **(2)** Excitatory effects for 10Hz will increase with number of pulses.

Secondary Objective: Examine rTMS spatial targeting: recruitment of specific networks in either dorsal (rTMS-D) or ventral (rTMS-V) pathways.

Secondary Endpoint: We predict that compared to the control condition, rTMS-D will enhance motion task performance and motion-related (high vs. low coherence) activity in the dorsal pathway (e.g., FEF, IPS), whereas rTMS-V will enhance motion-related activity in ventral pathway, with little or no effect on motion task performance.

Tertiary Objective: Establish rTMS brain state-dependency: stimulation of active versus inactive regions.

Tertiary Endpoint: We predict that rTMS effects on MT activity will be potentiated during motion task blocks compared to both color task and rest blocks.

3. Background & Significance:

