Subjects' side effects will be monitored closely. As indicated in the procedures section, side effects are assessed in a charted, structured interview both prior to and after the rTMS session. Subjects are informed of all known side effects during the consent process and during the rTMS sessions. They are further instructed during consenting and additionally at the conclusion of the rTMS session to contact the principal investigator or study physician with any questions or concerns (including those that may arise after the experimental session has ended).

Concurrent TMS-EEG Procedure. Before stimulating, the optimal right MT target is identified with fMRI activation and E-field modeling (see TMS setup in MRI-TMS, above), and co-registered on the subject structural MRI using the Brainsight neuronavigation system (Rogue Research, Montreal). Stimulation intensity is set on the MagPro R30 stimulator (MagVenture, Alpharetta, GA) at intensities scaled on motion disruption or motor thresholds.

Continuous EEG is recorded at 5000Hz with a 64-channel BrainAmp DC TMS-compatible EEG system (BrainProducts LLC, Morrisville, NC). The EEG cap is placed on the subjects' head and electrode impedances are adjusted before the start of each session to be less than 5kOhms. A figure 8 magnetic coil (A/P-MCF-B65, MagVenture) is placed as close as possible to the scalp (over the EEG electrodes) and held in place with a Robotic Arm System (RAS: Advanced Neuro Technology Co., Enschede, Netherlands), which provides precise fMRI-guided rTMS coil placement. The RAS, combined with a neuronavigation system (Brainsight Frameless, Rogue Research, Montreal, QC, Canada) automatically navigates the coil to cortical targets on the individual's 3-dimensionally rendered brain MRI with less than one millimeter error, and dynamically moves the coil to safely track with slight head movements in less than 0.3 seconds with millimeter precision while the subject performs the task. At the start of the experiment, the spatial location of each electrode is digitized and aligned on each individual's anatomical scan. After the concurrent TMS-EEG Session, a brief rTMS side effect rating scale and mood ratings will be administered before and after each rTMS session. Side effects will continue to be monitored throughout the procedure.

Specific Study Design Information

Study 1

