EEG analyses. Pre-processing of EEG includes bad channel replacement, temporal filtering, and ICA analyses to remove artifacts. EEG analyses use either repeated-measures ANOVAs or non-parametric methods (Maris and Oostenveld, 2007b, a) to infer amplitude and latency effects on relevant ERP components and/or sources, as described in each study. Coherence analyses are performed to estimate inter-channel connectivity, with planned analyses on cross-hemispheric and anterior-posterior associations. As done in our past studies, (Appelbaum et al., 2006; Appelbaum et al., 2008; Appelbaum et al., 2010; Ales et al., 2012; Appelbaum et al., 2012) depth-weighted minimum norm analyses will be performed using MRI-derived finite element head models calculated for each participant following alignment of electrode positions to the MRI head surface. Head models are based on compartmentalized tissue segmentations that defined contiguous regions for the scalp, outer skull, inner skull, and the cortex. Cortically constrained minimum norm source estimates are determined by a linear optimization of dipole magnitudes with the least total (root mean square) power while lead field normalization is used to compensate for the inherent bias toward superficial sources.

Specific Study Analytical Procedures

Study 1

TMS data: Mixed model ANOVAs with repeated-measures factors of Frequency (1Hz/5Hz/10Hz), and Number of Pulses (3/15/30 pulses), and rTMS (target, sham [vertex] stimulation) will be performed separately on the median RT and accuracy data. Power analysis shows that 30 subjects/group should be sufficient to see a medium sized effect at an alpha of 0.05. In our previous studies using a Working Memory task with active and sham rTMS over multiple sites, letter set sizes, and task phases, groups of 21 (Luber et al., 2007) 15 (Luber et al., 2008) and 26 (Luber et al., 2013) were sufficient to produce significant effects at the 0.05 level.

[figure not shown]
Study 2

DWI fiber tracking. Our DWI tractography methods have been reported (Davis et al., 2009). For a priori tracts connecting the MT cortex, we use TrackVis (trackvis.org) to identify MT and all connecting regions (FEF, IPS). (Kier et al., 2004b, a) FA values are extracted and analyzed using standard statistics.

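### Coherence between EEG channels can show a change in area MT amplitude as a change in connectivity, for channel pairs that both record that source

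*Combined protocol and SAP*

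**What the plan says.** The connectivity method is one sentence in Section 12, EEG analyses: "Coherence analyses are performed to estimate inter-channel connectivity, with planned analyses on cross-hemispheric and anterior-posterior associations". The level is the scalp channel. The sentence before it does mention sources, but for amplitude and latency effects on ERP components, not for coherence.

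The only cleaning described is this: "Pre-processing of EEG includes bad channel replacement, temporal filtering, and ICA analyses to remove artifacts". ICA is there to take out artifacts. The paragraph names no spatial filter, reference scheme, frequency band, analysis window or adjustment for amplitude.

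Source estimation follows in the same paragraph: "depth-weighted minimum norm analyses will be performed using MRI-derived finite element head models calculated for each participant". The coherence is not said to be computed on those sources.

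Section 2 predicts opposite effects of 1Hz and 5/10Hz on "motion-related (high vs low coherence) medial temporal (MT) activity (in both EEG, and fMRI" (coherence here means dot motion, not EEG). It adds "Excitatory effects for 10Hz will increase with number of pulses", and for Study 3: "We predict that rTMS effects on MT activity will be potentiated during motion task blocks compared to both color task and rest blocks". Section 12 carries the EEG methods into Study 3.

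**The concern.** Two scalp channels can record the same cortical source at the same instant. Ordinary coherence between them is then above zero with no coupling between areas, and it changes when that source becomes stronger or weaker relative to the noise.

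The trial's own hypotheses are that the strength of area MT differs by frequency, by pulse number and by brain state. The conditions to be compared for connectivity are therefore those in which amplitude is expected to differ. A cross-hemispheric or anterior-posterior difference found this way could be read as a network effect of rTMS when it may be the local amplitude effect again. For a project about circuits and spatial targeting, that matters to the interpretation.

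**Working it through.** The documents state no figure for EEG coherence, so there is nothing to reproduce. The check asks how far coherence moves when amplitude changes and coupling is absent.

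**Inputs from the documents.** 38 completers per study (Section 6); 40 trials per condition in Study 1 and 80 in Study 2 (Section 4); alpha 0.05 (Section 12, stated for the behavioural power analysis; two-sided is assumed).

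**Assumed inputs.** One shared source, unit-variance noise independent between channels, and no interaction. The source-to-noise power ratios a² and b² in the two channels, and the amplitude changes of 20% and 50%, are also assumptions.

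**Formula.** With source amplitude multiplied by g, magnitude-squared coherence is

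C = (g²ab)² / [(g²a² + 1)(g²b² + 1)].

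For equal channels with ratio s this is [g²s / (g²s + 1)]². At s = 1:

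- g = 0.8: (0.64/1.64)² = 0.152
- g = 1.0: (1/2)² = 0.250
- g = 1.2: (1.44/2.44)² = 0.348, a rise of 39%

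For g = 1.2, s = 0.5 gives 0.111 to 0.175 (+58%), and s = 2 gives 0.444 to 0.551 (+24%).

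**Unequal channels.** The last two columns give the share of 2,000 simulated studies in which a paired t-test on Fisher-z coherence was significant after a 20% rise. There was one test per study, and ratios were the same in all subjects.

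| a², b² | C at g = 0.8 | g = 1.0 | g = 1.2 | 40 trials | 80 trials |
|---|---|---|---|---|---|
| 1, 1 | 0.152 | 0.250 | 0.348 | 99.8% | 100% |
| 1, 0.25 | 0.054 | 0.100 | 0.156 | 92% | 99.6% |
| 1, 0.1 | 0.023 | 0.045 | 0.074 | 59% | 90% |
| 1, 0.01 | 0.002 | 0.005 | 0.008 | 6% | 13% |

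With a 50% rise, the last row becomes 27% at 40 trials and 60% at 80. With no amplitude change, the rate is 4% to 6% throughout.

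**Direction.** If the noise in the two channels is correlated at r, the numerator becomes (g²ab + r)². With r = 0.5 and ratios 1 and 0.01, a 20% rise takes C from (0.1 + 0.5)²/(2 × 1.01) = 0.178 to (0.144 + 0.5)²/(2.44 × 1.0144) = 0.168. Coherence falls although the source grew.

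**A measure blind to zero lag.** On the same simulated data, the imaginary part of coherency was significant in 3.9% to 5.7% of studies in every scenario, close to the nominal 5%.

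**What that measure does not solve.** If true lagged coupling exists and stays constant, imaginary coherency still scales with √[s₁/(s₁+1) × s₂/(s₂+1)]. From s = 1 in both channels (0.500), a 20% amplitude rise in one source gives √(0.590 × 0.5) = 0.543 (+9%), and in both gives 0.590 (+18%).

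**The case against.** Four points on the other side carry weight.

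- **Distance.** The target is right MT, and many cross-hemispheric or anterior-posterior pairs will be far apart. Where one channel hardly records the source, the effect is near the nominal rate at 40 trials. A reader might infer that the predicted amplitude change must appear as connectivity in every planned pair. The documents do not support that: they give neither the pairs nor the signal-to-noise ratios. But the plan does not restrict the pairs either, and a second channel with one tenth of the source-to-noise power still gives 59% to 90%.
- **Size of the change.** Section 2 predicts a change in the contrast between high and low dot coherence, not a 20% change in total source amplitude. The 20% is therefore illustrative. A change in that contrast does require changed activity on at least one trial type.
- **Pulse artifact.** Study 1 pulse counts run from 3 to 30, so it is tempting to say that artifact drives coherence. But pulses fall in the 3-s stimulation period, the motion period after it has none, and no coherence window is stated. ICA cleaning is planned. Table 2 also has conditions matched on pulse number (1 with 5, 2 with 4), and vertex conditions matched to 1 and 3. The artifact point holds only if coherence is computed during stimulation.
- **Importance.** No primary, secondary or tertiary endpoint is an EEG coherence measure. Other connectivity evidence is planned from fMRI beta-series correlations and DWI tractography.

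The vertex condition does not answer the main point, because the area MT change is predicted for stimulation of MT. Nor does the planned source estimation on its own: minimum-norm estimates leak between regions.

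**Conclusion.** The point stands in conditional form. The plan names inter-channel coherence as its EEG connectivity measure and gives no safeguard against a shared source. For pairs that both record area MT, a change in its amplitude alone can pass for changed connectivity.

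Under the stated assumptions, the chance of a spurious finding depends almost entirely on the pair, from near certainty to little above the nominal rate. Identical ratios in all subjects are an idealisation, and real rates will differ. In Study 2 the predicted changes lie in the dorsal and ventral pathways, so the 80-trial figures apply there to those sources by the same reasoning.

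A reader might conclude that coherence always follows source strength up and down. It does so for one source over independent noise, but shared background activity can reverse the sign. A reader might also conclude that the main results are compromised. They are not: the reaction-time, accuracy and regional-activity tests do not use this measure. What is at risk is the interpretation of the EEG connectivity results.

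**What to change.** Amend the EEG paragraph of Section 12 as follows.

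1. Base the planned cross-hemispheric and anterior-posterior inference on a measure insensitive to zero-lag mixing (imaginary coherency or weighted phase-lag index), preferably between the minimum-norm source regions already planned.
2. Compute it in the pulse-free motion period, or the equivalent interval in the color and rest blocks of Study 3.
3. Report source amplitude for the same contrast beside it, or adjust for it, since these measures still vary with signal-to-noise when true lagged coupling exists.
4. Match trial counts between conditions after artifact rejection. The design equalises them within each study (40, 80 and 60 per condition), but rejection can undo that.
5. Keep ordinary channel coherence as descriptive only.

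The cost is SAP wording and a different computation on data already collected and processed. The downside is that true zero-lag coupling will be missed, and the SAP should say so.
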